2.2 Secondary objectives

Key secondary objectives

Four key secondary objectives are identified a priori for special consideration in this study, in addition to the primary objective (superiority for HbA1c). A hierarchical closed testing procedure will be applied in order to control the type I error rate to support secondary superiority claims of dapagliflozin plus insulin treatment over placebo plus insulin treatment for the following key secondary objectives, for each dose of dapagliflozin:

- to examine whether treatment with dapagliflozin in combination with insulin is superior in reducing body weight or causing less weight gain as compared to placebo added to insulin treatment after 24 weeks of treatment.
- to examine whether treatment with dapagliflozin in combination with insulin leads to a lower absolute calculated mean daily insulin dose as compared to placebo added to insulin treatment alone, from baseline to week 24.
- to examine whether treatment with dapagliflozin in combination with insulin leads to higher percentage of patients with calculated mean daily insulin dose reduction from baseline to week 24 as compared to placebo added to insulin treatment
- to examine whether treatment with dapagliflozin in combination with insulin is superior in reducing Fasting Plasma Glucose (FPG) as compared to placebo added to insulin treatment after 24 weeks of treatment.

Other secondary objectives

Efficacy

To compare the effects of each dose of dapagliflozin versus placebo given as add-on therapy to insulin on additional weight and glycaemic outcome variables as well as changes in blood pressure and lipid values:

- Percentage change of calculated mean daily insulin dose from baseline to week 24
- Mean change in HbA1c from baseline to week 24 in patients with baseline HbA1c $\geq 9\%$
- Proportion of patients achieving a therapeutic glycaemic response defined as HbA1c $< 7\%$ at week 24
- Mean change in HbA1c from baseline to week 24 in patients with HbA1c $\geq 7.5\%$ and $< 9\%$ at baseline.
- Mean change in HbA1c from baseline to week 24 in patients with BMI ≥ 27 kg/m² at baseline.

- Mean change in HbA1c from baseline to week 24 in patients with BMI ≥ 30 kg/m² at baseline.
- Mean change in body weight from baseline to week 24 in patients with a baseline BMI ≥ 30 kg/m²
- Mean change in body weight from baseline to week 24 in patients with a baseline BMI ≥ 27 kg/m²
- Mean change in waist circumference from baseline to week 24

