3.5 Method of assigning subjects to treatment groups

After written informed consent has been obtained the patient will be assigned a E-code (country, centre, and patient specific). The E-code will be used to identify the patient throughout study participation. Patient eligibility will be established before treatment randomization.

A computer generated, stratified, block randomization schedule, containing stratum, randomization code and treatment, will be provided by AstraZeneca. The randomisation **will** be performed in two strata, one for patients with OADs and one for patients without OADs to ensure approximately equal numbers of patients across the treatment groups within each stratum. The randomization for both strata will be done within balanced blocks. The study medication will be packed according to this schedule.

Subject eligibility will be established before treatment randomization. Randomization to study treatment will be done on Visit 2, in OAD and non OAD strata. Subjects will be randomized strictly sequentially within each stratum, as subjects are eligible for randomization. If a subject discontinues from the study, the subject number will not be reused, and the subject will not be allowed to re-enter the study.

The number and size of tablets will be identical for the investigational products for the 4 treatment arms (applicable until week 12) and for the 3 treatment arms during long term extension period II starting after visit 12. Forced randomization is not allowed. If a patient is dispensed with a wrong drug supply, AstraZeneca must be immediately notified. Corrections for the patient will be made as required. Until resolution, the patient should continue taking study medication, but at the latest until the next scheduled visit.

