6.2 Description of outcome variables in relation to objectives and hypotheses

The primary objective of the study is to assess the efficacy of 2.5 mg, 5 mg and 10 mg dapagliflozin compared to placebo as add-on therapy to insulin in improving glycaemic control in subjects with type 2 diabetes who have inadequate glycaemic control on ≥ 30 IU injectable insulin daily for at least 8 weeks prior to enrolment, as determined by the change in HbA1c levels from baseline to week 24. The objective will be statistically analyzed using Dunnett's method (overall type I error rate for the primary endpoint 0.05). The significance level for each pair-wise group comparison of dapagliflozin versus placebo will be approximately 0.019.

Key secondary objectives are to compare the effects of each dose of dapagliflozin versus placebo given as add-on therapy to insulin after a 24-week double-blind treatment period by evaluation of:

1. The change in body weight from baseline to week 24
2. The absolute change in calculated mean daily insulin dose from baseline to week 24
3. The proportion of subjects with calculated mean daily insulin dose reduction from baseline to week 24

4. The change in FPG from baseline to week 24

The statistical testing of the primary and key secondary outcome variables will proceed in a sequential manner, to control the type I error rate within each dapagliflozin group at the 0.05 level. Specifically, the significance or non-significance of the treatment comparisons for the primary outcome variable will determine which, if any, statistical inferences are made for the key secondary outcome variables. Only those dapagliflozin groups significantly superior to placebo for the primary outcome variable will have statistical inference versus placebo for the first key secondary outcome variable, (1). Then, the testing for the other key secondary outcome variables will proceed so that

- the significance or non-significance of the treatment comparisons for (1) will determine which, if any, statistical inferences are made in treatment comparisons for (2), and
- the significance or non-significance of the treatment comparisons for (2) will determine which, if any, statistical inferences are made in treatment comparisons for (3), and
- the significance or non-significance of the treatment comparisons for (3) will determine which, if any, statistical inferences are made in treatment comparisons for (4).

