6.4 Method of statistical analysis

6.4.1 Analysis of primary and secondary efficacy for the 24-week treatment period

The primary and secondary efficacy analyses will be based on the full analysis set. The primary endpoint may also be analyzed with the per-protocol analysis set. Treatment effects will be determined through pair-wise treatment group comparisons: each dapagliflozin treatment group versus placebo. No statistical comparisons will be made amongst the dapagliflozin groups.

For endpoints not examining insulin dose, the last post-baseline measurement prior to the first up-titration will be used for subjects whose insulin dose is up-titrated (i.e., patients are censored at the time of up-titration). Endpoints examining insulin dose will also use LOC, but without censoring at the time of titration. To directly assess the relationship between changes in insulin dose and HbA1c, changes in HbA1c will also be summarized using the observations from the same time points as analyzed for insulin dose as a supportive analysis.

The change from baseline to week 24 in HbA1c will be analyzed using an analysis of covariance model (ANCOVA) with factors for treatment group and use of other OADs as fixed effects, and covariate for baseline HbA1c. The model will be used to derive least squares estimates of the treatment differences (each dapagliflozin dose group versus placebo) in mean change with corresponding p-value and two-sided 95% confidence interval. Further, two-sided 95% confidence intervals for the mean change within each treatment group will be calculated.

To preserve the Type I error rate ≤ 0.050 (two-sided) across the primary and within each dose group for the four key secondary endpoints, a hierarchical step-wise procedure will be used to interpret the statistical significance of these treatment comparisons. The details of the step-wise procedure are provided in Section 6.2.

Continuous secondary efficacy variables will be analyzed by means of an ANCOVA for change from baseline using treatment group and use of other OADs as fixed effects and baseline value as a covariate. By analogy to the primary efficacy variable, the model will be used to derive point estimates and two-sided 95% confidence intervals for the mean change within each treatment group as well as for the difference in mean change between the dapagliflozin and placebo groups. Nominal p-values for the difference between the treatment groups will be provided.

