When examining secondary endpoints defined within a subgroup (e.g., change in HbA1c in subjects with baseline HbA1c $\geq 9\%$, change in HbA1c in subjects with baseline HbA1c $\geq 7.5\%$ and $< 9\%$, change in HbA1c in subjects with baseline BMI ≥ 27 kg/m², change in HbA1c in subjects with baseline BMI ≥ 30 kg/m², absolute change in body weight in subjects with baseline BMI ≥ 27 kg/m², absolute change in body weight in subjects with baseline BMI ≥ 30 kg/m², absolute change in seated systolic BP and seated diastolic BP in subjects with baseline seated systolic BP > 140 mmHg), the same methods will be used.

Treatment effects on the primary endpoint will also be summarized within different subgroups to examine the robustness of the results across various categories of baseline characteristics. The two strata (with OADs and without OADs) will be considered subgroups. For this particular subgroup analysis, the interaction term between treatment and strata will be added to the ANCOVA model and tested for significance. Additionally, 95% confidence intervals of the treatment differences between each dapagliflozin group and placebo within each stratum will be provided. Other subgroups and their analyses will be outlined in the SAP.

The time course of all continuous variables will be presented using standard descriptive summary statistics calculated at each scheduled measuring time point and the last individual measuring time point. Moreover, standard descriptive summary statistics will be calculated for the absolute change from baseline to each scheduled measuring time point after baseline and the last individual measuring time point.

Discrete variables will be summarized by counts, proportions, and corresponding 95% confidence intervals. Comparisons between the treatment groups will be analyzed using two-sided Fisher's exact tests.

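### Key secondary (3), the only binary endpoint in the confirmatory hierarchy, is tested with an unstratified Fisher's exact test that is valid but gives away a few points of power

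*Protocol*

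**What the plan says.** Section 6.4.1 has one rule for all discrete variables: counts, proportions and 95% confidence intervals, and for the between-group test, "Comparisons between the treatment groups will be analyzed using two-sided Fisher's exact tests". It names no stratum and no covariate.

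Two week-24 efficacy endpoints fall under this rule.

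- Key secondary (3) in section 6.2: "The proportion of subjects with calculated mean daily insulin dose reduction from baseline to week 24". It is tested third of four in a fixed order intended "to control the type I error rate within each dapagliflozin group at the 0.05 level". Its result decides whether any inference is drawn on key secondary (4), the change in FPG.
- An endpoint that section 2.2 lists among the other secondary objectives: "Proportion of patients achieving a therapeutic glycaemic response defined as HbA1c" below 7% at week 24. It is outside the hierarchy and supportive only.

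Section 3.5 sets up two randomisation strata, with and without OADs, "to ensure approximately equal numbers of patients across the treatment groups within each stratum". The primary analysis is an ANCOVA with treatment, OAD use and baseline HbA1c. For the other continuous endpoints section 6.4.1 says: "Continuous secondary efficacy variables will be analyzed by means of an ANCOVA for change from baseline using treatment group and use of other OADs". That model also takes in each endpoint's own baseline.

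**The concern.** Key secondary (3) is the one member of the confirmatory hierarchy analysed without the factor that structured the randomisation. It is also the one tested by a method known to run below its nominal level. With 150 to 200 patients per arm there is no small-sample reason for an exact test, unless responses turn out to be rare.

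What is at stake is power. A dose that misses narrowly at step (3) loses the insulin-reduction claim and, by the sequence, any FPG claim. The protocol also names no between-group estimate with a confidence interval for this endpoint, whereas the continuous ones get an adjusted difference and 95% CI.

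**Working it through.** **Inputs from the protocol.** Two-sided 0.05 within each dose for the key secondaries (6.2). 153 evaluable per arm, 5% non-evaluable, 161 per arm and 644 in total planned (6.5). 808 actually randomised (synopsis and 6.5). Allocation 1:1:1:1 (3.1). No response rate is given for any binary endpoint, so all rates below are assumptions.

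**The plan's own figure.** For HbA1c with difference 0.5, SD 1.2 and alpha 0.019, the normal approximation is n = 2 × 1.2² × (2.3455 + 1.2816)² / 0.5² = 151.6, so 152. With the noncentral t, 153 per arm gives power 0.9001. Then 153/0.95 = 161.05, about 161, and 4 × 161 = 644. The sample size reproduces and is not affected by this point.

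**Patients per arm for the binary test.** Planned: 153. Actual: 808/4 = 202 if split evenly, or 202 × 0.95 = 191.9, about 192, after the protocol's 5% allowance.

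**Exact size and power.** For each test, sum over all responder counts a and b the product Bin(a; n, p1) × Bin(b; n, p0) wherever that test gives p ≤ 0.05. Setting p1 = p0 gives the true size.

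| True size at nominal 5% | Rate 5% | 10% | 20% | 30% | 40% |
|---|---|---|---|---|---|
| Fisher, n = 153 | 2.5% | 3.3% | 3.6% | 3.7% | 4.0% |
| Chi-square, n = 153 | 4.8% | 5.0% | 5.1% | 5.1% | 5.3% |
| Fisher, n = 202 | 2.9% | 3.4% | 3.7% | 3.9% | 3.8% |

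| Assumed rates | Fisher / chi-square power, n = 153 | n = 192 | n = 202 |
|---|---|---|---|
| 5% vs 12% | 52.9 / 60.1 | 63.8 / 70.7 | 66.6 / 72.2 |
| 5% vs 15% | 80.7 / 85.1 | 89.1 / 92.1 | 90.8 / 93.1 |
| 10% vs 20% | 64.0 / 69.6 | 74.8 / 79.3 | 77.3 / 81.1 |
| 20% vs 33% | 69.3 / 73.5 | 79.7 / 82.7 | 81.9 / 84.6 |
| 30% vs 45% | 74.4 / 78.1 | 84.0 / 86.4 | 85.6 / 87.8 |
| 11% vs 25% | 87.1 / 90.2 | 93.8 / 95.3 | 94.9 / 96.2 |

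The loss at 153 per arm is about 4 to 7 points, and 3 in the best-powered row. At 192 to 202 per arm it is about 1 to 7 points.

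**An example.** At 192 per arm, take 33 responders against 19. The pooled rate is 52/384 = 0.135, the standard error is √(0.135 × 0.865 × 2/192) = 0.0349, and z = (14/192)/0.0349 = 2.09, so the chi-square p is 0.037. Fisher's p is 0.052, and the sequence for that dose would stop.

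**Where the loss comes from.** The comparison above uses an unstratified chi-square, so it isolates Fisher's discreteness. The stratum and baseline were examined by simulation (2,500 trials per scenario, 153 per arm, two near-equal strata). The stratum effects correspond to odds ratios of 1, 1.6 and 2.7 (log odds 0, 0.5, 1.0).

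| Scenario (average rates) | Fisher | Chi-square | CMH | Logistic, stratum + baseline |
|---|---|---|---|---|
| No stratum effect, 10% vs 21% | 68.7 | 74.4 | 74.4 | 74.8 |
| Stratum OR 1.6, 11% vs 22% | 70.7 | 76.0 | 76.1 | 76.8 |
| Stratum OR 2.7, 12% vs 23% | 70.6 | 75.9 | 76.8 | 77.2 |
| Stratum OR 1.6, strongly prognostic baseline, 8% vs 16% | 46.4 | 52.4 | 52.5 | 60.8 |

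Moving from chi-square to CMH gains at most 0.8 points. Adding baseline gains about 8 points, but only in the last row, where its effect was assumed to be strong. Across the null scenarios the rejection rates were 2.7-3.4% for Fisher, 4.1-5.1% for CMH and 4.2-5.4% for the logistic test.

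**The case against.** The best defence is that nothing here is wrong. Fisher's test holds its level after stratified randomisation, so the 0.05 claim in section 6.2 stands. The ANCOVA rule is expressly for continuous variables and the discrete rule is separate and clear, so the protocol does not contradict itself. At the size actually reached, several scenarios lose only 1 to 3 points. Replacing a confirmatory test after 808 patients have been randomised, in order to gain power, also carries a credibility cost. All of this stands, and it limits the point to efficiency and consistency.

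Four stronger readings are tempting but not supported.

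- A reader might infer that omitting the stratum is what makes the test conservative. The simulation attributes under 1 point to the stratum; discreteness accounts for most of the loss.
- A reader might infer a large gain from logistic regression. One simulation of HbA1c below 7% (assumed 25% vs 11%, 3,000 trials) gave 86% for Fisher, 89% for CMH and 94% for a likelihood-ratio logistic test. That logistic test rejected 6.8% of the time under the null, so its power is not comparable. The excess did not recur in the simulation above, and the endpoint is not confirmatory. The protocol does not say how prognostic baseline insulin dose is for key secondary (3).
- A reader might blame Fisher for the risk to the FPG claim. Any test in third place gates FPG; Fisher only makes a miss at that step somewhat more likely.
- A reader might infer that the change is free. It alters protocol text and exchanges an exact test for an asymptotic one.

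**Conclusion.** The point holds as a modest, worthwhile improvement to one confirmatory endpoint. It is not an error of validity. The test fixed in section 6.4.1 for key secondary (3) has a true size of about 2.5-4% at nominal 5% for response rates of 5-40%. It gives up about 4-7 power points at the planned 153 per arm and about 1-7 at 192-202 per arm. At 10% vs 20% with the numbers actually randomised, power is 75-77% instead of 79-81%.

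The power figures rest on assumed response rates, an even split of the 808 and the protocol's own 5% allowance. The case for stratifying is mainly agreement with the randomisation and with the other endpoints, since its contribution to power is under 1 point. The HbA1c below 7% endpoint is supportive and comes in only for consistency.

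**What to change.** Before the 24-week data are unblinded, amend the discrete-variable rule in section 6.4.1 as follows.

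- Test key secondary (3), and for consistency HbA1c below 7%, with a CMH test stratified by OAD use. Report a stratum-adjusted risk difference with 95% CI for each dose against placebo.
- Give logistic regression with treatment, OAD use and the relevant baseline value (insulin dose or HbA1c) as a supportive analysis.
- Keep Fisher's exact test for sparse tables, with the condition for using it fixed in advance.

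No new data are needed. Because the rule stands in the protocol, the change goes through the amendment process in section 7.4, and any SAP text must match it. The statistical cost is small: an asymptotic test can slightly exceed 5% (up to 5.3% for the chi-square at 153 per arm above, and 5.1% for CMH in simulation). The document does not show whether the 24-week unblinding has already happened. If it has, Fisher should remain the confirmatory test and the stratified analysis should be reported as supportive.

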6.4.2 Analysis of efficacy during the long-term, double-blind extension period I and II

All variables to be analyzed at week 24 will be re-examined at the week 48 and 104 time point. Further, changes from week 48 to week 104 will be analyzed (see Section 4.6). In addition, the change in HbA1c levels from week 24 to week 48 and 104, and from week 48 to week 104 will be evaluated (see Section 4.6). In general, the same statistical methodology as described for the 24-week treatment period will be used for data in the long term double-blind extension period I and II. Summaries will be limited to point estimates and 95% confidence intervals.

For extension period II, summaries will be provided by the original, randomized treatment groups although selected analyses will also provide results for the pooled group of all patients who received 10 mg during this period

6.4.3 Analysis of Pharmacokinetics

The dapagliflozin plasma concentrations obtained by sampling of individual subjects will be used to build a population pharmacokinetic model to estimate pharmacokinetic parameters (e.g. CL/F, Vd/F and k_a). Possible covariate effects on PK parameters (e.g. gender effect on CL/F) may be identified and quantified. The estimated pharmacokinetic parameters will be used to compute individual exposure measures (e.g. AUC, C_{min}). Relationships between these exposure measures and efficacy endpoints (e.g. changes from baseline in HbA1c) will be explored. Similar exploratory analyses may be performed for other efficacy and safety measures. The pharmacokinetic data and efficacy endpoint responses derived from this study may be pooled with similar data from other studies to refine the modelled exposure-response relationship. Listings and summary statistics will be reported for pharmacokinetic parameters and exposure measures. The pharmacokinetic analysis will be described in a separate report

6.4.4 Analysis of safety

The safety evaluations will include analyses of AEs, laboratory parameters, ECG, vital signs, hypoglycaemic events, calculated creatinine clearance, eGFR, total protein/creatinine ratio (mg/g) oedema and physical examination. The analysis of safety will be based on the safety analysis set. Safety data gained during the 24-week treatment period, the long term double-blind extension period I and II as well as during the 3-week follow-up period will be evaluated. Safety variables will be summarized descriptively.

For extension period II, summaries will be provided by the original, randomized treatment groups although selected analyses will also provide results for the pooled group of all patients who received 10 mg during this period.

6.5 Determination of sample size

Each pairwise treatment group comparison will be tested at a significance level of approximately 0.019, according to Dunnett's method, in order to maintain an overall type I error rate < 0.050 for the primary objective. To detect a difference of 0.5% between each dapagliflozin group versus placebo for changes from baseline to week 24 in HbA1c, assuming a SD = 1.2%, and at a two-sided significance level of 0.019, 153 evaluable subjects are needed in each treatment group to provide 90% power. Assuming that 5% of the subjects will not be evaluable in the full analysis set, 161 subjects per treatment group (644 subjects total) are planned for randomization.

Approximately 700 patients will be offered to enter the long-term extension period II. This estimate is based on the number of actually randomised patients (808) and the assumption that approximately 14 % of the randomised patients will have been withdrawn at week 48 (visit 12).

6.6 Interim analyses

Summaries of long-term safety data may be produced during the long-term double-blind extension period II to support regulatory submissions if the study is not yet completed. These summaries will be conducted on safety data collected until a pre-specified cut-off date, regardless of observation time of each subject. The summaries will be descriptive. No formal statistical hypothesis testing will be performed and efficacy data will not be analysed.

Investigators, patients, and study monitors will continue to be blinded until completion of the study without any knowledge of the treatment codes, except for cases of medical emergencies.

Safety parameters to be analysed, will have the following rules applied.:

For summary at a time point using observed values (e.g. safety labs at week 65) to be presented, there should be at least 10 subjects with non-missing observations in at least one treatment group.

